Developing and Evaluating Product Messaging

Hypotheses and Analytic Plan

NCT# NCT04716010

Version Date: 6/01/21

Hypotheses

The overall purpose of this study is to assess the impact of taxes, warnings, and a combination of taxes and warnings on US adults' decisions to purchase products that contain red meat in an online grocery store.

Primary Outcomes

The co-primary outcomes are the count of products that contain red meat and the percent of products in the shopping basket that contain red meat. We will report both count and percent of products that contain red meat.

We hypothesize that:

1. Compared to the control (no taxes and no warnings), both taxes and warnings will lead to reduced purchases of products that contain red meat.
2. The combination of taxes and warnings will lead to a larger reduction in purchases of products that contain red meat than taxes or warnings alone.

Secondary Outcomes

We hypothesize that the taxes condition, warnings condition, and taxes and warning condition will lead to:

Behavioral

- A) Decrease in total saturated fat of products purchased
- B) Decrease in total sodium of products purchased
- C) Decrease in total calories of products purchased

Psychological

- D) Decrease in perceived healthfulness of eating red meat
- E) Increase in perceived risk of cancer from eating red meat
- F) Increase in perceived environmental harms of eating red meat
- G) Increase in thinking about the health harms of food products
- H) Increase in thinking about the environmental harms of food products
- I) Increase in thinking about the price of food products
- J) Decrease in perceived healthfulness of specific red meat products
- K) Increase in perceived environmental harm of specific red meat products
- L) Increase in perceived cost of specific red meat products
- M) Increase in intention to reduce red meat consumption

Other Outcomes reported by condition

We hypothesize that the taxes condition, warnings condition, and taxes and warning condition will lead to:

- N) Increase in policy support for taxes on red meat products
- O) Increase in policy support for health warnings on red meat products
- P) Increase in policy support for environmental warnings on red meat products

Other Outcomes not reported by condition

- Q) Acceptability of the online grocery store
- R) Ease of use of the online grocery store

STATISTICAL CONSIDERATION

Statistical Methods

First, we will conduct a soft launch of 200 participants. With the data from the 200 participants, we will run descriptive analyses of the primary, secondary, and other outcomes, and we will confirm randomization is working properly.

If randomization is working properly and there are not apparent issues with the data collection (e.g. technical issues with the online store software), we will resume data collection until the final sample is achieved. The original 200 participants from the soft launch will be included in the final dataset.

If randomization is not working properly and/or there are apparent issues with the data collection (e.g., erroneous skip patterns), we will address all identified issues then resume data collection until the final sample is achieved. The original 200 participants from the soft launch will not be included in the final dataset.

We will descriptively report unadjusted values for primary, secondary, and other outcomes.

We will use a two-sided critical alpha of 0.05 to conduct all statistical tests. Per CONSORT guidelines, we will not test for balance in covariates. Primary analyses will be intent-to-treat, including all eligible participants with non-missing outcome data (e.g., complete-case).

Sensitivity Analyses

We will describe dropout (defined as entering the store but not completing the purchasing task) by study arm and by screener characteristic (age, red meat consumption). If differential dropout is identified, we will consider sensitivity analyses to handle missing outcome data, such as inverse probability weighting.

For all primary, secondary, and other outcomes, we will assess whether the outcomes vary by study arm with regression models, in which the referent group will be the control (compared to each of the three interventional study arms). For the primary outcomes, the regression model will be selected based on the frequency of zero purchases of products containing red meat. If the frequency of zeros is high (>10% of participants), we will consider models to deal with the high proportion of zeros (e.g., zero-inflated Poisson or zero-inflated negative binomial for a count variable; fractional regression for percentage variable). Choice of model will also depend on whether heteroscedasticity exists. Model selection exercises will be reported. For secondary and other outcomes, we will use linear regression.

For all analyses, means will be compared between each of the treatment groups and the control group, and for the primary outcome all pairwise comparisons of means will be examined. We will consider a result statistically significant at $p < 0.05$.

In exploratory analyses, we will examine whether the following participant characteristics moderate the intervention effects on the primary outcomes:

- a. Frequency of red meat intake
- b. Interest in health
 - For interest in health, we will take the average of the 3 items if $\alpha > .70$. The 3 items are adapted from Hearty et al. (2006). If α is not above .70, we will either create a scale excluding the item that makes the three-item scale drop below .70, if there is one; or we will look at the items separately.
- c. Interest in sustainability
 - For interest in sustainability, we will take the average of the 6 items if $\alpha > .70$. The six items are adapted from Haws et al. (2014). If α is not above .70, we will either create a scale excluding the item(s) that make(s) the six-item scale drop below .70, if there is one; or we will look at the items separately.
- d. Household income level
- e. Educational attainment

- f. Age group
- g. Race/ethnicity
- h. Political orientation
- i. Gender

To test whether these characteristics moderate the effect of the intervention on the count or percentage of products containing red meat selected, we will fit a series of regression models (one for each potential moderator), with trial arm, the moderator (specified as dummy variables), and their interaction as predictors. We will use a Wald chunk test to determine the joint interaction. We will quantitatively evaluate the presence of moderation by calculating the marginal effect of the intervention on the outcome at different levels of the moderating variable. If the pattern of main results is similar between intervention arms (warning label, tax, and warning plus tax), we will consider combining intervention arms for the moderation analysis.

Sample Size and Power

Sample size calculations were conducted using PASS 2019 Power Analysis and Sample Size Software (NCSS, Kaysville, Utah, USA). The effect size for the warning label was hypothesized to be the smallest effect size, and so the sample size was chosen to power this effect. With this sample size, the power associated with the tax and combined conditions will be maintained at approximately the same level or higher (better).

For a factorial design with two factors at 2 and 2 levels, assuming a Cohen's *d* of 0.1 (considered "small" (Cohen, 1988), and conservative relative to SSB warning label experiments which found 0.25 (Grummon & Hall, 2020)), the sample size per arm needed to achieve 80% power at an alpha level of 0.05 is $n=786$ per arm ($n=3,144$ total across the four arms).

Outliers and Exclusions

To complete the shopping task, a participant's shopping basket must have +/- 2 items of the total number of items on the shopping list. There are 9 items total on the shopping list, so the participant's basket must have 7-11 items.

We will conduct sensitivity analyses excluding individuals who are in the bottom 2 percentile of expenditures, those who complete the study unusually quickly (e.g., based on the distribution of time to completion as ascertained during a soft launch of the study), and individuals who are non-compliant with the shopping list (<50% of products selected comply with the shopping list).

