Sample size calculations were conducted using PASS 2019 Power Analysis and Sample Size Software (NCSS, Kaysville, Utah, USA). The effect size for the warning label was hypothesized to be the smallest effect size, and so the sample size was chosen to power this effect. With this sample size, the power associated with the tax and combined conditions will be maintained at approximately the same level or higher (better). For a factorial design with two factors at 2 and 2 levels, assuming a Cohen's d of 0.1 (considered "small",²⁸ and conservative relative to SSB warning label experiments which found 0.25),²⁹ the sample size per arm needed to achieve 80% power at an alpha level of 0.05 is $n=786$ per arm ($n=3,144$ total across the four arms).

Outliers and Exclusions

To complete the shopping task, a participant's shopping basket must have +/- 2 items of the total number of items on the shopping list. There are 9 items total on the shopping list, so the participant's basket must have 7-11 items.

We will conduct sensitivity analyses excluding individuals who are in the bottom 2 percentile of expenditures, those who complete the study unusually quickly (e.g., based on the distribution of time to completion as ascertained during a soft launch of the study), and individuals who are non-compliant with the shopping list (<50% of products selected comply with the shopping list).

SAFETY MANAGEMENT

Provided that this study is conducted completely online, and participants do not have any interactions with study staff there is no anticipation of adverse events. However, the investigators have provided an email to contact as well as the IRB contact information, on the consent form, should a participant be concerned about any aspects of the research study.

DATA COLLECTION AND MANAGEMENT

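### The 80% power, and the same or higher power claimed for the combined condition, do not carry over to hypothesis 2, whose pairwise contrasts have about 34% to 51% power at the plan's own effect size.

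*SAP*

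**What the plan says.** **Hypothesis.** The SAP (Hypotheses, Primary Outcomes) numbers two primary hypotheses. The second is that combining taxes and warnings gives a "larger reduction in purchases of products that contain red meat than taxes or warnings alone". The protocol does not number its hypotheses, but its synopsis also plans comparisons between intervention arms for the primary outcomes.

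**Analysis.** Under Statistical Consideration the SAP sets the error rate: "We will use a two-sided critical alpha of 0.05 to conduct all statistical tests". Control is the referent in the regression models. In addition, "for the primary outcome all pairwise comparisons of means will be examined", and "We will consider a result statistically significant at" p<0.05. The protocol has the same text. Neither document says which contrasts must succeed for hypothesis 2 to be supported.

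**Power.** Both documents carry the same Sample Size and Power section. It begins: "The effect size for the warning label was hypothesized to be the smallest effect size, and so the sample size was chosen to power this" (the warning effect). It continues: "With this sample size, the power associated with the tax and combined conditions will be maintained at approximately the same level or higher (better". No comparator is named. The calculation is described as a factorial design with two factors at two levels each and d = 0.1, and "the sample size per arm needed to achieve 80% power at an alpha level of 0.05" is given as 786 (3,144 in total). No effect size is given for the tax, for the combination, or for what warnings add to a tax.

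**The concern.** The power argument is that the warning effect is the smallest, so every other condition has at least as much power. That holds for a comparison with control: the combined arm should differ from control by more than the warning arm does. It does not hold when the combined arm is compared with the tax arm. Both arms then carry the tax, and the expected difference is only what warnings add. That is d = 0.1 if the effects add and less if they overlap.

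A second issue compounds this. The 80% appears to belong to a factorial main effect, which pools two arms on each side, while the plan tests one arm against another.

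Hypothesis 2 is one of two primary hypotheses. A reader who takes 80% or more as its power could read a non-significant combination v tax result as evidence that warnings add nothing to a tax, when the trial had about an even chance of missing an increment of the planned size. With no stated rule, it is also left open whether beating only one of the two single policies counts as support.

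**Working it through.** **Inputs from the documents:** 786 per arm, equal allocation, two-sided alpha 0.05, d = 0.1 for the warning label, 2x2 factorial basis for sizing, pairwise contrasts in the analysis. **Assumptions:** SD = 1, normal approximation, no loss of data, tax d from 0.10 to 0.25, and effects that add unless stated otherwise.

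**1. Reproduce the plan's figure.**
- Two-group size for d = 0.1: 2 x (1.960 + 0.842)² / 0.1² ≈ 1,570 per group.
- In a 2x2 main effect each group is two arms, so 1,570 / 2 = 785 per arm. The F test with one numerator degree of freedom and f = 0.05 gives 79.98% at 785 and 80.03% at 786. This matches the stated 786.
- An arm-against-arm comparison would need 1,570 per arm. So the 80% is the power of 1,572 v 1,572.

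**2. Pairwise power at 786 per arm.**
- SE of a difference = sqrt(2/786) = 0.0504 SD.
- At 0.10: 0.10 / 0.0504 = 1.982, and Φ(1.982 − 1.960) = 50.9%.
- At 0.05: 0.05 / 0.0504 = 0.991, and Φ(0.991 − 1.960) = 16.6%.
- Detectable with 80% power: (1.960 + 0.842) x 0.0504 = 0.141 SD.

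**3. Both hypothesis 2 contrasts.** If effects add, combination v tax equals the warning effect and combination v warnings equals the tax effect. The contrasts share the combination arm, so their correlation is 0.5. Joint power comes from the bivariate normal.

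| Tax d | Combination v tax (0.10) | Combination v warnings | Both |
|---|---|---|---|
| 0.10 | 50.9% | 50.9% | 34.2% |
| 0.15 | 50.9% | 84.5% | 47.8% |
| 0.20 | 50.9% | 97.8% | 50.7% |
| 0.25 | 50.9% | 99.9% | 50.9% |

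A simulation with 200,000 replicates gave 34.2% and 50.7% for both at tax d = 0.10 and 0.20. If only half the warning effect remains on top of a tax (increment 0.05), power for both is 6.7% to 16.6% over the same tax range.

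**4. What the missing rule could allow.** Suppose warnings add nothing to a tax. The chance that at least one of the two contrasts is significant in favour of the combination depends on what warnings do alone:

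| Tax d | Warnings alone d = 0.1 (combination v warnings = tax − 0.1) | Warnings alone d = 0 |
|---|---|---|
| 0.10 | 5% | 51% |
| 0.15 | 18% | 84% |
| 0.20 | 51% | 98% |
| 0.25 | 84% | 99.9% |

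If both contrasts are required, the chance is at most 2.5% in every row. The first column of results uses the plan's own warning effect; the second contradicts it.

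**5. Comparison with control.** With tax d = 0.10 and additive effects, combination v control is d = 0.20, with 97.8% power. For that comparison the sentence on the combined condition is well supported.

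**The case against.** **The power sentence is not tied to hypothesis 2.** This stands. The sentence names no comparator, control is the referent in the models, and against control it is reasonable for the combined arm. It is still the only power statement about that arm, and hypothesis 2 is the only numbered primary hypothesis specific to it, so the comparator should be named.

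**Combination v tax has the same power as warnings v control.** Under additivity this is correct: both are 50.9%. A reader might infer that combination v tax falls short of the power for the warning effect. It does so only with overlap, or when both contrasts must succeed; with tax d of 0.15 or more the joint figure is 48% to 51%, and the 34% needs the boundary case where the tax effect is no larger than the warning effect. The shortfall is against the stated 80%, and most of it comes from the factorial v pairwise mismatch. With 1,570 per arm, combination v tax would reach 80% under additivity.

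**The either-contrast risk.** A reader might infer that the plan lets hypothesis 2 be declared almost automatically from the tax effect. The documents do not support that. Being larger than one or the other alone ordinarily means larger than each, and the text says a result is significant at p<0.05, not that one significant contrast proves the hypothesis. Both contrasts are already planned. The highest percentages also need warnings to have no effect at all, against the plan's d = 0.1. What remains is missing detail.

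**Conclusion.** The point holds as a power statement that needs correcting. The stated 80% does not apply to the pairwise contrasts that test hypothesis 2. At d = 0.1 for the warning increment, power is about 51% for combination v tax and 34% to 51% for both contrasts. It is at most about 17% if the increment is 0.05. The smallest increment over a tax detectable with 80% power is 0.14 SD.

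These figures rest on additivity, on a tax effect that the documents do not give, and on no loss of data; losses would lower them. Synergy would raise them, but the documents assume none. The absence of a both-contrasts rule is a lesser matter of clarification. On the plan's own warning effect, an either-contrast reading would produce an unwarranted claim about 5% to 84% of the time across tax d = 0.10 to 0.25, against at most 2.5% when both are required.

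**What to change.** 1. **Sample Size and Power, both documents.** Limit the sentence on the tax and combined conditions to comparisons with control. State that the 80% at 786 per arm is for a factorial main effect, and give the pairwise power beside it.
2. **Same section.** State hypothesis 2 power separately: about 51% for combination v tax at an increment of 0.1, 34% to 51% for both contrasts, at most about 17% at an increment of 0.05, and 0.14 SD detectable with 80% power. Name the assumptions (additive effects, assumed range for the tax effect).
3. **SAP, Hypotheses and the pairwise-comparison text; the latter also in the protocol.** As a clarification, say that hypothesis 2 is supported only if the combination is lower than tax and lower than warnings, each at two-sided p<0.05. Requiring both needs no split of alpha between the two contrasts. If only one is met, report that contrast without claiming hypothesis 2.

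This costs wording only, with no new data or added sample. The downside is a less favourable stated power for the combined condition and a hypothesis that is harder to claim. Keeping 80% for both contrasts would instead need about 1,570 to 1,958 per arm (6,280 to 7,832 in total) under additivity; the wording change does not depend on that.

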Following online consent, participants will be randomized to one of the four arms by Gorilla and enter into Lola's Grocery. In this online grocery store, participants will complete a shopping task. They will be asked to select items using a pre-determined nine-item shopping list (see below), and they will be informed that their budget is \$40. To complete the shopping task, a participant's shopping basket must have +/- 2 items of the total number of items on the shopping list (7-11 items). After completing the shopping task, participants will be redirected to a survey. In the survey, participants will answer standard behavior and reaction measurement questions, as well as standard demographic questions. Prior to the shopping task, participants will be informed that 1 in 10 participants will actually receive, via mail, the groceries they select and the remainder of their shopping budget (\$40). The purpose of this is to incentivize participants to make purchases that reflect their real-life shopping habits. However, in reality, we will send 1 in 10 participants a gift card of \$40 (the shopping task budget). At the end of the survey, we will inform the 1 in 10 participants that the panel vendor will be sending them a gift card

rather than groceries and ask for their email address. The panel vendor will email the gift card.

Shopping List:

1. 1 pizza
2. 1 burrito
3. Burger patties (meat or vegetarian)
4. Breakfast sausages (meat or vegetarian)
5. 1 frozen individual meal
6. 1 loaf of bread
7. 1 sandwich filling (for example, ham, turkey, or peanut butter)
8. 1 pack of tortillas
9. 1 taco filling (for example, steak, chicken, or beans)

Subject Completion/Withdrawal Procedures

A study participant is determined to have completed the study when they have finished and exited the study survey. To withdraw their data from the study, a participant would have to contact the study team or the university IRB.

Screen Failure Procedures

Prior to entering into the study, individuals will complete a survey screener. If the individual is younger than 18 years old, does not live in the United States, does not eat red meat at least one or more times per week, or does not do at least half of the grocery shopping for their household, they will be deemed ineligible. Such participants will be redirected to a screen notifying them that they are ineligible for the study.

SCREENING AND MONITORING EVALUATIONS AND MEASUREMENTS (how measurements will be made)

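### Does an intent-to-treat label on a complete-case primary set, with the missing-outcome analysis left optional, call for a change?

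*SAP*

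**What the plan says.** The SAP (Statistical Methods) and the Protocol (Statistical Methods) carry the same sentence on the analysis set: "Primary analyses will be intent-to-treat, including all eligible participants with non-missing outcome data (e.g., complete-case".

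Under Sensitivity Analyses, the SAP commits the team to "describe dropout (defined as entering the store but not completing the purchasing task) by study arm and by screener characteristic (age, red meat consumption", and continues: "If differential dropout is identified, we will consider sensitivity analyses to handle missing outcome data, such as inverse probability weighting".

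Three other places fix the timing:

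- Protocol, Study Steps: after consent, "participants will be randomized to one of the four arms by Gorilla and enter into" the store. Allocation therefore precedes the task.
- SAP, Outliers and Exclusions: for the task to be complete, the "basket must have 7-11 items".
- Protocol, Subject Completion/Withdrawal Procedures: "A study participant is determined to have completed the study when they have finished and exited the study survey". This is a later point than the end of shopping, where the dropout definition stops.

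**The concern.** Randomisation protects the comparison of everyone allocated. It does not protect the comparison of those who go on to finish a task. Inclusion here depends on an event after allocation, and the arms could plausibly affect it. Two arms add 30% to the price of red meat products against a $40 budget and a seven-item minimum, and two arms show warnings to regular red meat eaters. If an arm changes who finishes, the primary contrasts shift by an unknown amount in an unknown direction. The design effect is only 0.1 SD, so a small shift could matter.

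The safeguard also looks weak. Differential dropout has no threshold or test, no weighting model is given, and even a plain imbalance obliges the team only to think about an analysis. Loss between the shopping task and the end of the survey falls outside the definition of dropout. That loss would affect secondary outcomes D to M and other outcomes N to P.

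**Working it through.** **The plan's own figure.** For a main effect in a 2x2 factorial with d = 0.1, two-sided alpha 0.05 and 80% power, the normal approximation gives 2 x (1.960 + 0.842)^2 / 0.1^2 = 1,570 per factor level, or 785 per arm. The noncentral t gives power 0.7998 at 785 and 0.8003 at 786. The stated 786 per arm (3,144 in total) reproduces. It contains no dropout allowance, and the documents do not say whether it counts people randomised or completers.

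**Inputs.** From the documents: 786 per arm and two-sided alpha 0.05. Assumed, because the documents give neither: dropout rates, and the gap between leavers and completers in SD.

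**Bias.** With p the share of an arm lost and delta its leaver-minus-completer gap, the complete-case contrast is off by p1 x delta1 - p0 x delta0. If delta is the same in both arms, this is excess dropout x delta.

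**False rejection of one contrast with no true effect.** For 786 completers per arm, SE = sqrt(2/786) = 0.0504. If 786 are randomised and control loses 10%, there are 707 control completers against 692, 668 or 629.

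| Excess dropout x gap | Bias (SD) | 786 completers | 786 randomised |
|---|---|---|---|
| 2 points x 0.25 SD | 0.005 | 5.1% | 5.1% |
| 5 points x 0.5 SD | 0.025 | 7.9% | 7.5% |
| 10 points x 1.0 SD | 0.10 | 50.9% | 44.6% |

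**Would a difference be seen?** If identified meant a two-sided 5% test between two arms of 786, the chance of flagging it would be 24% for 10% v 12%, 85% for 10% v 15%, and above 99.9% for 10% v 20%. The harsh row of the table would almost never go unnoticed.

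**Unequal gaps.** The table assumes the same delta in both arms. If both arms lose 10% but only one loses selectively, by 0.5 SD, the bias is 0.10 x 0.5 = 0.05 SD. Then 0.05/0.0504 = 0.99, and false rejection is 16.8% (15.6% with 707 per arm). A trigger based on unequal rates would miss this.

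**What weighting could recover.** Suppose both arms lose 10%, and one of them loses 13% of heavy and 7% of light red meat eaters, half of the sample each. Heavy eaters are then 0.5 x 0.87/0.90 = 0.4833 of that arm's completers, a shift of 0.0167 SD for each 1 SD between the two groups. Weighting on red meat consumption by arm removes that part. It removes nothing that age and red meat consumption do not explain.

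**Survey loss.** Outcomes D to M are 10 of the 13 secondary outcomes. With N to P that makes 13 of the 16 non-primary outcomes compared by arm. The store records the basket (Protocol, Screening and Monitoring Evaluations and Measurements), so leaving during the survey does not by itself remove either co-primary outcome.

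**The case for a change.** The best case for a change is that describing dropout does not tell a reader how far it could move the result. Deciding whether and how to analyse it after seeing the data leaves avoidable discretion. The example of equal rates with selective loss sharpens this: 0.05 SD is half the design effect, and a rate comparison would not reveal it. Replacing the conditional promise with a firm one would cost little.

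Part of this stands. The trigger is undefined and the promise is soft, and a firmer sentence would do no harm. But the discretion covers a sensitivity analysis and leaves the primary estimate untouched. The case that a rate trigger misses is also one where obligatory weighting helps only so far as age and red meat consumption predict leaving. A delta analysis would reach further, but the documents offer nothing on which to set its range. An anchor from the 200-person soft launch would compare intake groups rather than leavers with completers, and with an assumed split of 100 and 100 its precision would be about 1.96 x sqrt(2/100) = 0.28 SD.

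On the label, a reader is told complete-case in the same sentence, so new wording would change no result.

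**Conclusion.** No change follows. What remains is missing detail in a secondary safeguard, and analysts can fill it sensibly. The plan already obliges them to show dropout by arm and by the two screener variables, and gives them a method. Because it compares means, a reader with those counts can apply the bias formula above under any gap thought plausible. Survey loss will show in the number of participants each complete-case regression uses, and it concerns only secondary and other outcomes.

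The size is open. Under a common gap the assumed cases run from 0.005 to 0.10 SD, and that upper figure is not a ceiling if gaps differ between arms. Nothing in the documents makes any of these values likely. A single session of 20 to 30 minutes with an incentive on completion points towards low dropout. Bias is therefore a risk and has not been shown.

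The conclusion rests on two things: that unfinished baskets give no primary outcome, which the documents strongly imply but do not state, and that the promised description of dropout is delivered. If that description showed large or clearly unequal loss, the weighting the plan names would be the natural next step under the existing text.
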